# 3.2.2. Maintenance Phase (Visit 4-6)

The goal of the Maintenance Phase is to characterize the PK under steady-state study conditions as well as demonstrate the safety of PF-06412528 over a 2-6 week period. If at Visit 4 subjects require additional pain relief in the opinion of the investigator, they will continue in the study for an additional 2-4 weeks (Visit 5 and/or Visit 6) up to 6 weeks total.

Daily Diary and in-clinic pain intensity and safety will be assessed at each visit to determine if any dose adjustments are required. Rescue medication (acetaminophen and/or NSAID's) is permitted during this phase. IR morphine for rescue is discouraged during the Maintenance Phase.

Blood samples will be collected for PK analysis at Visit 4 for those subjects that achieve a stable dose between Visits 3a-d. Two blood samples will be taken at least two-hours apart at Visit 4. If for any reason PK samples are not obtained at Visit 4, the subject should return to enable them to be obtained at an unscheduled visit.

At the final Maintenance Phase visit (Visit 4 or 5 or 6), the investigator will discontinue the subject's PF-06412528 therapy and convert the subject back to their standard of care of opioid therapy. Blood samples will be collected for PK analysis if not already obtained. A Post-Treatment/End of Study visit will be scheduled in 7 ±2 days (Visit 7).

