nen	Concomitant Medication (Diary Review)			X	X	X	X	X	X	X	
eatı	Study Drug Use (Diary Review)			X	X	X	X	X	X	X	
Ţ	Adverse Events (Diary review)			X	X	X	X	X	X	X	
	Plasma Sample (Section 7.5.2) 							X		X 	
Careg	iver Training and Subject Instruction		X								
Dose	Conversion Calculation 		X								
Dispe	nse Study Drug		X	X	X	X	X	X	X		
Prescribe Rescue Medication (as necessary)			X	X	X	X	X	X	X	X	
Dose Titration (as needed)				X	X	X	X				
Drug Accountability				X	X	X	X	X	X		
Early Withdrawal Subjects 										X	
Weekly Telephone call 			<						· 		>

Min = Minimum; Max = Maximum; NR = Not Required; EOS = End of Study; ECG = Electrocardiogram; ET = Early Termination; COWS = Clinical Opiate Withdrawal Scale; PK = Pharmacokinetics, Wks= Weeks

- 1. Visit 3a is a mandatory visit.
- 2. Visits 3b, 3c, and 3d are required only if further dose titrations are required to reach a stable dose. Subjects must reach a stable dose of PF-06412528 on or before Visit 3d to be eligible to start the 6-week Maintenance Phase. Unscheduled visits during the Treatment Period for purposes of dose adjustment will, at a minimum, require a NRS pain scale and a COWS score on subjects. An unscheduled visit for an AE will require performing the Visit 6 procedures.
- 3. Informed consent must be provided by the subject's caregiver (parent or legal guardian). Subjects are required to provide their assent.
- 4. Review the subject's pre-study standard of care (SOC) therapy and record on the appropriate case reporting form.
- 5. SOC therapy is required to stop on this visit. Record these changes on the appropriate case reporting form.
- 6. Serum pregnancy test for a qualified female of childbearing potential (Section 7.3).
- 7. Urine pregnancy test for a qualified female of childbearing potential (Section 7.3).
- 8. ECGs performed post-baseline are acceptable when performed "for-cause".
- 9. Refer to Section 7.4.1 for the correct Columbia-Suicide Severity Rating Scale to apply for a given age group.
- 10. Record serious adverse events from the signing of the informed consent. Non-serious AEs are recorded from first dose of study drug. Review and transcribe Caregiver adverse findings from the Daily Diary to the appropriate case reporting form. Follow up on all SAEs through and including 28 calendar days post the last dose of study drug (Section 8.2). Follow up requirements for non-serious AEs (Section 8.1).

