- 11. Review all sections of the Daily Diary as part of the Caregiver Training and Subject Instruction. Issue a new diary at each scheduled visit. Weekly phone contact between visits to review diary entries. Call must be documented in source.
- 12. Two plasma samples for PK analysis will be collected at least 2 hours apart.
- 13. Request PK samples (Section 7.5.1) of early termination subjects if not acquired at Visit 4.
- 14. Consult Appendix 2 of the protocol for the PF-06412528 Conversion Guide. The investigator must figure the conversion to PF-06412528 by Visit 2.
- 15. Subjects prematurely withdrawing from the Treatment Period regardless of reason (eg, failure to achieve a stable dose, lack of efficacy, AE) are requested to fulfill the Visit 6 procedures and activities. Early withdrawal subjects will be converted back to their pre-study SOC medication or alternate pain therapy, at the discretion of the investigator.
- 16. Weekly telephone contact with the caregiver must be documented in source.

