# 3.2.1. Conversion/Titration Phase (Visits 2-3d)

Subjects and their caregiver(s) will report for weekly visits during this 1-4 week period to convert their current standard of care opioid therapy for pain management to PF-06412528. The goals of the Conversion/Titration Phase are to convert subjects from their pre-study standard of care opioid analgesic to PF-06412528 and to individualize pain management by titrating PF-06412528 (Visits 2-3d; see Schedule of Activities) to achieve a stable dose. A stable dose is characterized as a dose that provides adequate analgesia and minimizes adverse reactions for 5 to 7 days. During Visit 2 the subject's study eligibility will be verified, the subject's current standard of care opioid therapy will be discontinued and PF-06412528 will be initiated at a dose determined using the PF-06412528 Conversion Guide (Appendix 2).

Four weekly scheduled study visits (Visits 3a-3d) are planned to provide enough time to individualize pain management with PF-06412528. Visit 3a is mandatory for all subjects and Visits 3b, 3c, and 3d are optional, if additional dose titration is needed. Visits 3b or 3c or 3d can be skipped if a subject reaches a stable dose at a prior visit. When a stable dose is achieved, the subject advances to the Maintenance Phase at the next visit (Visit 4). More frequent consultation with the investigator as well as additional unscheduled clinic visits are permitted, as needed (eg, to titrate study drug). All information about the dosing of PF-06412528 (ie, dosage strength, frequency of dosing, and daily schedule) will be obtained and recorded at each scheduled/unscheduled visit.

The Conversion/Titration Phase will end once a PF-06412528 dose that provides adequate analgesia and minimizes adverse reactions is achieved (ie, stable dose) with infrequent need for IR morphine as rescue as determined by the investigator. Subjects who do not reach a stable dose without the need for IR morphine as rescue by Visit 3d, will be removed from treatment and converted back to their previous opioid therapy or another therapy at the discretion of the investigator.

The start of the Maintenance Phase will begin once a subject has achieved a stable dose of PF-06412528 and the next study visit (Visit 4) will be scheduled in two weeks' time.

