# 9.2. Efficacy Analysis

Analgesic effect analyses will be performed using all available in-clinic pain intensity data from the safety population (see Section 9.4). The baseline pain intensity score will be the score from the in-clinic assessment at Visit 2.

Pain intensity scores will be summarized descriptively by study week and phase of the Treatment Period (Conversion/Titration Phase and Maintenance Phase). Actual scores and the change and percentage change from baseline will be calculated.

Rescue medication or additional analgesic medication use over time will be summarized descriptively.

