8.3. Efficacy Analysis

Analgesic effect analyses will be performed using all available in-clinic pain intensity data from the safety population... The baseline pain intensity score will be the score from the in-clinic assessment at Visit 2.

Pain intensity scores will be summarized descriptively by study week and phase of the Treatment Period (Conversion/Titration Phase and Maintenance Phase). Actual scores and the change and percentage change from baseline will be calculated.

Rescue medication or additional analgesic medication use over time will be summarized descriptively.

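### Pain means by study week average different children each week, chosen partly by their response, so a drift may be misread as a change in pain over time

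*Protocol*

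**What the plan says.** **Who is seen during titration.** All children attend Visit 3a. Beyond that, a footnote to the Schedule of Activities says "Visits 3b, 3c, and 3d are required only if further dose titrations are required to reach a stable dose". Protocol 3.2.1 adds: "Subjects who do not reach a stable dose without the need for IR morphine as rescue by Visit 3d, will be removed from treatment". Another footnote to the Schedule gives examples of reasons for early withdrawal: "eg, failure to achieve a stable dose, lack of efficacy, AE".

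**Who is seen during Maintenance.** Protocol 3.2.2 states: "If at Visit 4 subjects require additional pain relief in the opinion of the investigator, they will continue in the study". It then makes the last treatment visit variable: "At the final Maintenance Phase visit (Visit 4 or 5 or 6), the investigator will discontinue the subject's PF-06412528 therapy". Other places describe the length differently. The Schedule footnote on titration visits and SAP 2.1 refer to a six-week Maintenance Phase, and Protocol 3.2 gives a Treatment Period of 7 to 10 weeks.

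**How pain is analysed.** Protocol 9.2: "Pain intensity scores will be summarized descriptively by study week and phase of the Treatment Period" and "Actual scores and the change and percentage change from baseline will be calculated". SAP 8.3 repeats this, "using all available in-clinic pain intensity data from the safety population", with Visit 2 as baseline. Protocol 7.1.1 keeps diary scores out of the analysis. SAP 7 refers to imputation rules for safety endpoints and handles PK concentrations, but has no rule for pain. Neither document plans a fixed-cohort summary or one by last visit.

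**Status.** The Protocol Summary lists analgesic effect under Other endpoints. SAP 4.1 proposes no hypothesis.

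**The concern.** A table of means by week invites the reader to look down the column and see a course over time. That works only if the same children, or a comparable group, contribute to each row. Here attendance depends on response at two stages. In titration, children with good control skip visits, and those never controlled are removed. After Visit 4, on the plain reading of Protocol 3.2.2, children judged to need more pain relief stay and others may stop. The two stages can push the later weekly means in opposite directions, so the net direction cannot be predicted. Change from baseline is computed within each child, but its weekly mean is still taken over a changing group.

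At stake is how the pain table in the study report is read: an apparent loss or gain of analgesia over the weeks could be selection alone.

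**Working it through.** **1. No planned figure to reproduce.** Neither document gives an SD, sample size or precision for pain. The relevant counts, in Protocol 9.1, are about 140 enrolled and at least 100 with two weeks of Maintenance. Since 1 − 100/140 = 28.6%, 40 children could leave before that point with the target still met. Stops at Visit 4 come on top.

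**2. Calendar.** Scheduled in-clinic scores by nominal day, from the Schedule of Activities:

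| Day | Children with a scheduled score |
|---|---|
| 7 | All (Visit 3a) |
| 14 | Only those not stable at 3a |
| 21 | Visit 3c (still titrating) and Visit 4 of the 3a-stable; none for the 3b-stable |
| 28 | Visit 3d and Visit 4 of the 3b-stable |
| 35 | Visit 5 of the 3a-stable who continued and Visit 4 of the 3c-stable |
| 42 | Visit 5 of the 3b-stable who continued and Visit 4 of the 3d-stable |
| 49 | Visit 6 of the 3a-stable and Visit 5 of the 3c-stable, continuers only |
| 56 | Visit 6 of the 3b-stable and Visit 5 of the 3d-stable, continuers only |
| 63, 70 | Visit 6 of the 3c-stable and 3d-stable respectively, continuers only |

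The mixing of groups follows from the schedule itself, before any dropout. Day 7 is the only on-treatment week planned for every child.

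**3. Upper bound for the Visit 4 step.** If exactly the fraction f with most pain continues, mean pain rises by SD × φ(z_f)/f with no change in anyone. Here z_f is the normal cut-off for the top fraction f. For f = 0.7, 0.5 and 0.3 the factor is 0.50, 0.80 and 1.16.

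- SD 2 (assumed): 1.0, 1.6 and 2.3 points.
- SD 1 (assumed, for a narrower spread once a stable dose is reached): 0.5, 0.8 and 1.2 points.
- SD 2 and a correlation of 0.5 between score and decision: half the first line, 0.5 to 1.2 points.

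**4. Simulation on the calendar.** Every input here is an assumption.

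- Baseline pain has mean 5 and SD 1.5. On-treatment change has mean −1.5 and SD 1.5 and is constant over time. Scores are limited to 0–10.
- About 40% become stable at each titration visit (45% in the run without selection). About 50% continue at Visit 4, and again at Visit 5.
- Selection lowers the log-odds of stability and raises the log-odds of continuing, by 0.5 (mild) or 1 (moderate) per SD of on-treatment pain. The single-step runs use 1.
- The true on-treatment mean is 3.54 to 3.55 throughout. Early-termination scores are left out, because the plan assigns them to no week.

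Mean pain by day:

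| Scenario | 7 | 14 | 21 | 35 | 49 | 70 |
|---|---|---|---|---|---|---|
| No selection | 3.54 | 3.53 | 3.54 | 3.54 | 3.53 | 3.52 |
| Mild | 3.55 | 3.94 | 3.61 | 3.56 | 4.01 | 4.76 |
| Moderate | 3.55 | 4.25 | 3.62 | 3.56 | 4.19 | 5.07 |
| Titration selection only | 3.54 | 4.25 | 3.62 | 2.98 | 2.99 | 4.24 |
| Visit 4 rule only | 3.55 | 3.55 | 3.55 | 4.04 | 4.80 | 5.06 |

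False drifts in mean pain:

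- Mild: 4.01 − 3.55 = +0.46 at Day 49.
- Moderate: 5.07 − 3.55 = +1.52 at Day 70.
- Visit 4 rule only: 4.80 − 3.55 = +1.25 at Day 49.
- Titration selection only: 2.99 − 3.54 = −0.55 at Day 49.

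Mean change from baseline drifts by about half as much. Under moderate selection it goes from −1.45 at Day 7 to −0.71 at Day 70, a shift of 0.74. Under titration selection only it goes from −1.46 to −1.72 at Day 49, a shift of −0.26.

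The largest drifts fall where few children remain. Scaled to 140 enrolled, the moderate run has about 19 children at Day 49 and 3 at Day 70.

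**5. Percentage change.** It is undefined at a baseline of 0 and unstable near it: one point is 1/1 = 100% from a baseline of 1, but 1/8 = 12.5% from 8. Protocol 4.1 sets no minimum NRS score, and the children are already on opioids.

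**The case against.** The strongest reply is that the plan claims little here. Pain is a descriptive Other endpoint, and a weekly observed mean correctly describes the children seen that week. This stands, and it sets the weight of the point. A reader might infer that the table is wrong, or that this flaw is what stops the study showing analgesic effect. The documents support neither reading. They promise no such demonstration, and an open-label single-arm study with titration and rescue could not attribute a change to the drug under any tabulation. What remains is that the table may be misread.

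A reader might also infer that children stay past Visit 4 only if they still need relief. Protocol 3.2.2 does not contain that restriction. The phrase could mean a continuing need for an analgesic rather than a high score, and children who stop go back to standard opioid therapy, so stopping does not show that the need has ended. The stated durations conflict as well: stability at Day 7 plus 14 days gives a stop at Day 21, or 3 weeks, against the 7-week minimum in Protocol 3.2. Under either meaning continuation depends on pain status, but the link to the score may be weak.

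A third tempting inference is that falling pain during titration could be dropout. The main documented mechanism points the other way: Visits 3b to 3d hold children not yet stable, and the simulated mean rises at Day 14. Withdrawal for lack of efficacy can occur earlier, but those children are due a pain score at Visit 6/ET, which counts among the available data.

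On percentage change, entry requires confirmed moderate-to-severe pain and the usual opioid is withheld on the day of Visit 2, so baselines of 0 may be rare. Absolute change is already planned. This part is minor.

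**Conclusion.** The concern holds as a reporting weakness. That weekly means average different, response-selected children follows from the schedule and the stopping rules, without any numerical assumption. The size does rest on assumptions: roughly 0.5 to 1.5 NRS points of false drift in mean pain under the selection strengths tried. It reached about 1.5 upwards and about 0.55 downwards, and was close to zero in some weeks. The 2.3-point figure is a sharp-selection extreme (top 30% continue, SD 2) and should not be quoted as expected.

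The primary safety and PK objectives are untouched. This is a worthwhile and cheap improvement, not a condition for running the study. Separately, Protocol 3.2.2 must be reconciled with the Schedule footnote, Protocol 3.2 and SAP 2.1 on the length of Maintenance; which rule is right is not a matter for this review.

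**What to change.** Amend SAP 8.3. Protocol 9 lets the SAP modify plans for secondary endpoints and reserves amendments for major changes to the primary endpoint, so a SAP edit should suffice for an Other endpoint.

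1. Add fixed-cohort summaries of change: Visit 2 to Visit 3a in all children with both scores, and Visit 2 to Visit 4 in all who reach Visit 4.
2. Summarise Maintenance pain by last-treatment cohort (last dose at Visit 4, 5 or 6, or early termination), each against its own baseline. Define the cohorts from last-dose date and disposition. The Visit 6/ET label cannot separate them, because Protocol 3.3 and 6.2.2 send Visit 4 leavers and early terminators through the same procedures.
3. Add one row for the last on-treatment in-clinic score in all safety subjects, early-termination scores included, with the reason for leaving.
4. Keep the weekly means, but show n for each week, state the week to which early-termination scores belong, and draw no conclusion over time from them.
5. Make absolute change the main measure. Give percentage change as a median, with the number excluded for a baseline of 0.

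The cost is one or two extra tables from scores already collected. The last-dose cohorts will be small and are themselves defined by outcome, so they too remain descriptive.

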# **Document History**

Document	Version Date	Summary of Changes					
Amendment 2 26 May 2015		A substantial change will be preceded by (SC). All other changes are administrative changes as required by the latest protocol template.					
		Title					
		Removed the word " chronic " from the title and throughout the protocol, to improve recruitment by expanding the subject population to subjects with moderate-to-severe post-surgical pain requiring around-the-clock opioid therapy based on investigators feedback.					
		Protocol Summary					
		Endpoints					
		Primary  • (SC) Pharmacokinetics: volume of distribution (Vd/F) deleted and changed to "average concentration at steady-state (Css, av)," the low fluctuation in plasma concentration-time profile of morphine and the sparse PK Sampling schedule do not support an estimation of Vd/F analysis.  Study Design					
		Added					
	Safety Assessment						
		Pharmacokinetic Assessment					
		Safety Analysis					
		
 
Pharmacokinetic Analysis         (SC) Pharmacokinetics: Vd/F added here data permitting.     
 
					
		Sections 3.3 and 6.3: (SC) Added PK collections to Visit 6/ET, to accommodate PK sample at early withdrawal if not obtained at Visit 4, which was not provided in Amendment 1.					
		Section 4.1 Inclusion Criteria					
		2. (SC) "confirmed moderate-to-severe chronic pain (of cancerous or non-cancerous origin) requiring around-the-clock treatment with an opioid analgesic for an extended period of time." changed to "confirmed moderate-to-severe pain requiring around the-clock treatment with an opioid analgesic, "to remove "chronic and allow for the recruitment of post-surgery subjects."					
		3. (SC) "5 consecutive days" changed to "3 consecutive days" to expand the subject population and to align with the post-surgical days requirement.					

Most post-surgery subjects will be switched to an extended release opioid within 48 to 72 hours if around-the-clock treatment with an opioid analgesic is required.

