#### Section 4.2 Exclusion Criteria

- **8.** (SC) "Undergone major surgery within past 30 days..." **changed to** "...past 3 days....," based on feedback from Embeda investigators, subjects are not likely to be treated with ER opioids for 30 days.
- **11.** (SC) **Clarified** "subject endorses a 4 or 5 on the Columbia Suicide Severity Rating Scale," to be consistent throughout the protocol.
- **12.** (SC) **Added** "History of sleep apnea with the past year..., additional safety measure.
- 13. (SC) Added ALT and AST  $\geq$ 3 x upper limit of normal..., additional safety measure.
- **14.** (SC) **Added** "Epidural opioid <2 hours prior to the first dose of study drug," additional safety measure to prevent respiratory depression.
- **15.** (SC) **Added** "Planned surgery during the course of the study," additional safety measure.
- **Section 4.3** Life Style Changes wording is **modified**, to adjust the pregnancy wording for the age group of the subjects.
- **Section 5.2** Subject Compliance wording is **modified**, to set guidelines to aid the investigator.
- **Section 5.6** Study Drug Accountability is **modified**, to set guidelines to aid the investigator.
- **Section 5.7** (SC) Concomitant medications **modified**, to clarify allowed and prohibited medications.
- **Section 6.2** Treatment Periods description is **modified**, to simplify the protocol.
- **Section 6.3 Addition** and description of Early Termination Visit and Procedures, to ensure final safety assessments are performed and PK sample for subjects who withdraw if not done are obtained.
- **Section 6.4 Combined** Post Treatment Visit 7 and End of Study Visit 8, to reduce the duration from 21 days to 7 days post the Last Treatment Visit.
- **Section 6.5** Subject Withdrawal is **modified**, to provide more details to aid investigator in handling subjects who withdraw.
- **Section 6.6** Lost to Follow-Up is **modified**, to provide more details to aid investigator.
- **Section 8.4** Medication Errors is **modified and moved**, to provide more clarity.
- Section 8.11 Occupational Exposure is added, to provide

		guidance for possible AE.
		Section 9 Data Analysis/Statistical Methods
		(SC) Deleted "Unless otherwise indicated, any statistical tests performed will be 2-sided and differences resulting in a p-value ≤0.05 will be considered statistically significant," as there are no statistical analyses performed in the study.

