# 3.3. Post-Treatment Period/End of Study Period

The purpose of the Post-Treatment Period/End of Study (Visit 7) is to perform safety assessments  $7 \pm 2$  days after the last dose of PF-06412528 at Visit 6.

Subjects who discontinue early from the study as well as subjects who complete 2 weeks of PF-06412528 during the Maintenance Phase and have their last dose of PF-06412528 at Visit 4 will complete the Visit 6/Early Termination procedures without the need to return for the Post Treatment/End of Study Visit.

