#### Visit 6/Early Termination

During this visit the following procedures will be followed for all subjects:

- Physical examination.
- Serum pregnancy test.
- Clinical Laboratory Test (Hematology, blood chemistry and urinalysis): See Section 7.2.3.
- Follow the same procedures and assessments as described at Visit 3a, (except do not perform the urine pregnancy test, instead a serum pregnancy test should be performed at this visit): See Schedule of Activity and Section 7.3.

- Obtain plasma samples for PK analysis (only if not acquired at Visit 4): Record the following items on the appropriate CRF:
  - The exact dosing date and clock time for the morning and previous 3 doses of PF-06412528, and
  - The exact clock time of the blood draw for the 2 samples.
- Subjects who discontinue early from the study as well as subjects who complete 2 weeks of PF-06412528 during the Maintenance Phase and have their last dose of PF-06412528 at Visit 4 will complete the Visit 6/Early Termination procedures without the need to return for the Post Treatment/End of Study Visit.
- Schedule Post Treatment/End of Study Visit, if required.

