# **6.3. Early Termination Visit**

Subjects who do not reach a stable dose at Visits 3a-3d will proceed to the Early Termination Visit. Subjects who do not complete 2-weeks of the PF-06412528 treatment at their maintenance dose for any reason will proceed to the Early Termination Visit.

All subjects including subjects who discontinue early from the study will complete the procedures specified for Visit 6/Early Termination (see Section 6.2.2).

### 6.4. Post Treatment/End of Study (EOS) Visit 7

Approximately 1 week after discontinuing PF-06412528 and initiating dose conversion back to the subject's standard of care therapy, subjects will undergo the Post-Treatment/End of Study procedures, which will consist of an assessment of any **AEs** since the previous visit and the **suicidality assessment**.

The following procedures will include:

- SIB Assessment: C-SSRS (Section 7.4).
- AE assessment.

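### Section 3.2.2 returns every child who finishes Maintenance to opioid therapy, with no allowance for a child whose pain has resolved

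*Protocol*

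**What the plan says.** Protocol Section 3.2.2 governs the end of treatment for every child who finishes Maintenance, whether at Visit 4, 5 or 6. At that visit "the investigator will discontinue the subject's PF-06412528 therapy and convert the subject back to their standard of care of opioid therapy". Earlier in the same section, children continue beyond Visit 4 if the investigator judges that they need further pain relief. The section then schedules Visit 7 for 7 ±2 days later, whichever visit was the last.

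Section 6.4 describes the same step as stopping study drug and "initiating dose conversion back to the subject's standard of care therapy", without the word opioid.

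The rules for children who leave early are looser. Under Section 3.2.1, a child with no stable dose by Visit 3d is "converted back to their previous opioid therapy or another therapy at the discretion of the investigator". The Visit 3d text in Section 6.2.1 makes conversion depend on need, refers to an analgesic and leaves the choice to the investigator. Footnote 15 of the Schedule of Activities allows another pain therapy, at the investigator's discretion, after premature withdrawal.

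On follow-up, Section 3.3 says that early leavers, and children whose last dose is at Visit 4, "will complete the Visit 6/Early Termination procedures without the need to return for the Post Treatment/End of Study Visit". Section 6.2.2 repeats this and adds that Visit 7 is to be scheduled if required. The SAP is silent on conversion at the end of treatment.

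**The concern.** Amendment 2 dropped the requirement that pain be chronic, in order to "allow for the recruitment of post-surgery subjects". Such pain can be expected to ease in some children over the weeks of the study. The exit instruction in Section 3.2.2 still assumes that every child needs an opioid when study drug stops. An investigator who correctly declined to restart one would be departing from the text.

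What is at stake is an unnecessary opioid prescription for a child. The opposite hazard matters too: after weeks of daily morphine a child should not stop abruptly, so the instruction cannot simply be deleted.

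**Working it through.** There is no sample-size or power figure to reproduce. The check compares the texts and then works out the visit timing.

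**1. What each group of children is offered when study drug stops**

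| Child | Place in Protocol | Depends on need | Alternative named | Investigator discretion |
|---|---|---|---|---|
| Finishes Maintenance | 3.2.2 | No | No | No |
| Same child, at follow-up | 6.4 | No | No, but the word opioid is absent | No |
| No stable dose by Visit 3d | 3.2.1 | No | Yes | Yes |
| No stable dose at Visit 3d | 6.2.1 | Yes | Yes | Yes |
| Premature withdrawal | Schedule, footnote 15 | No | Yes | Yes |

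Children who finish Maintenance are the only group given none of the three in explicit words.

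**2. Can a child whose pain has resolved reach this rule?**

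- Inclusion 2 asks for moderate-to-severe pain needing continuous opioid treatment, with no chronicity condition.
- Inclusion 3 asks for 3 consecutive days of opioid immediately before first dosing.
- Exclusion 8 bars surgery only within 3 days before first dosing.
- Section 3.2.2 makes continuing past Visit 4 depend on a need for further pain relief. By implication, those who stop at Visit 4 include children judged not to need it.

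The first part of Section 3.2.2 therefore releases such a child, and the last part sends the child back to an opioid.

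**3. Timing**

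Minimum days of opioid use at a visit on Day D = 3 pre-dose days (inclusion 3) + (D − 1), assuming uninterrupted dosing. D is the nominal day in the Schedule of Activities.

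| Stable dose reached at | Final visit 4 | Final visit 5 | Final visit 6 |
|---|---|---|---|
| 3a | Day 21: 3 + 20 = 23 | Day 35: 3 + 34 = 37 | Day 49: 3 + 48 = 51 |
| 3b | Day 28: 3 + 27 = 30 | Day 42: 3 + 41 = 44 | Day 56: 3 + 55 = 58 |
| 3c | Day 35: 3 + 34 = 37 | Day 49: 3 + 48 = 51 | Day 63: 3 + 62 = 65 |
| 3d | Day 42: 3 + 41 = 44 | Day 56: 3 + 55 = 58 | Day 70: 3 + 69 = 72 |

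Section 1.6 cites a workshop report that relatively few children are given continuous opioids beyond 4 weeks, which is 28 days. Nominally, 11 of the 12 combinations exceed 28 days. At the early edge of the ±2 day window, Day 28 becomes Day 26 and gives 3 + 25 = 28, so 10 of 12 exceed it throughout the window. The rule thus applies mostly at durations that the protocol itself describes as uncommon in children. This makes resolved need plausible by the final visit, but it does not count the children concerned.

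**4. Follow-up**

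For a last dose at Visit 4, Section 3.2.2 schedules Visit 7, while Sections 3.3 and 6.2.2 waive it. Once conversion becomes optional, the waiver would fall on the children most likely to be tapered or stopped. Visit 7 is where Section 6.4 places the adverse event and suicidality assessments.

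**The case against.** The strongest reply is that Section 3.2.2 is a design description and not the operating instruction. The Schedule refers the reader to the procedures and assessments sections for detail. The Visit 6/Early Termination procedures in Section 6.2.2 contain no order to convert to an opioid, and the Schedule has no row for it. Section 6.4 says only standard of care therapy, which the treating clinician normally decides. This stands as a reason to expect little harm in practice. It does not supply a condition, because no text tells the investigator that conversion may be omitted for a child who finishes Maintenance.

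A second reply is that the contrast with early leavers has a reason. Those children failed titration or withdrew, so another analgesic is an obvious need, whereas finishers were stable on morphine. Section 1.6 calls the study children opioid-dependent, and after at least 23 days of opioid a return to the prior drug is a sensible default. This also stands. It supports keeping that option and guarding against abrupt cessation, but it does not support making conversion compulsory.

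A third reply is that the scheduling line in Section 6.2.2 (Visit 7 if required) settles the Visit 7 conflict in favour of the waiver. It may do so as the text stands. That is a reason not to resolve the conflict by simply adopting the waiver once tapering or stopping is allowed.

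**Conclusion.** The point holds as a minor safety correction. Section 3.2.2 states an unconditional rule that gives the wrong result for a child whose need for an opioid has ended. It rests on two readings: that children stopped at Visit 4 include some judged not to need further relief, and that pain resolves on study in some eligible children. Both are reasonable inferences, but neither is stated outright.

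The number affected is unknown and no estimate is made. Endpoints, sample size and analyses do not change.

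Two stronger readings are not supported:

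- A reader might take the Amendment 2 remark that "subjects are not likely to be treated with ER opioids for 30 days" as proof that need will have ended. It explains the change to the surgery exclusion and concerns extended-release opioids only. A child stepping down to an immediate-release opioid fits it equally well.
- A reader might take the planned 100 children with at least 2 weeks of Maintenance as the number at risk. That counts children covered by the rule, not children harmed by it.

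**What to change.** Reword the sentence in Section 3.2.2, with matching words in Section 6.4, along these lines:

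> The investigator will discontinue PF-06412528 and, if needed and at the investigator's discretion, convert the subject to their prior opioid or another analgesic therapy, or taper opioid therapy; opioid therapy should not be stopped abruptly.

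This extends to finishers the flexibility already written in Section 6.2.1 for Visit 3d, keeps return to the prior opioid available, and adds a guard against abrupt cessation. The procedures in Sections 6.2.2 to 6.4 contain no taper schedule, so the manner of tapering would rest on the investigator's judgment.

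In Sections 3.3 and 6.2.2, except from the Visit 7 waiver any child who is tapered or stopped at Visit 4, so that the contact at 7 ±2 days in Section 3.2.2 is kept for them.

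The cost is a few sentences, plus one visit that Section 3.2.2 already plans for each child so excepted. No new analysis is needed.
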